### **2.1.3.10 On-treatment assessment/event and observation periods**

For adverse event reporting the overall observation period will be divided into three mutually exclusive segments:

1. ***pre-treatment period***: from day of subject’s informed consent to the day before first administration of study treatment
2. ***on-treatment period***: from date of first administration of study treatment to 130 days (approximately five terminal half-lives of canakinumab/pembrolizumab) after the date of last administration of study treatment
3. ***post-treatment period***: starting at day 131 after the date of last administration of study treatment

Safety summaries (tables, figures) and summaries of on-treatment death include only data from the on-treatment period with the exception of baseline data which will also be summarized where appropriate (e.g. change from baseline summaries). In addition, a separate summary for death including on treatment and post treatment deaths will be provided. In particular, summary tables for adverse events (AEs) will summarize only on-treatment events, with a start date during the on-treatment period (***treatment-emergent*** AEs).

An ***on-treatment assessment*** is defined as any assessment performed after the date of first administration of study treatment i.e. assessments performed in the following time interval (including the lower and upper limits): from date of first administration of study treatment +1 up to 130 days after the date of last administration of study treatment.

In case at time of the analysis, the date of last administration of study treatment is missing, on-treatment adverse event/assessment include any adverse event/assessment recorded in the database which occur after the start date of the study treatment.

However, all safety data (including those from the post-treatment period) will be listed and those collected during the pre-treatment and post-treatment period will be flagged.

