All assessments including C1D1, during the treatment period (except tumor assessments)	± 3 Days (-3 days for Cycle 1 Day 1)
Canakinumab injection (if applicable)	± 3 Days
Pembrolizumab infusion (if applicable)	± 3 Days
PK/IG/PD sampling	Refer to tables in Section 8.5.1
26, 52, 78 and 104 day safety follow-up visits	± 7 Days
130-day safety follow-up visit	+ 14 Days
EOT	≤ 21 Days after permanent discontinuation of study treatment, but before the surgery
EOT biomarker sampling	At time of surgery if possible, if not within 4 days prior to surgery

Subjects should be seen for all visits/assessments as outlined in the assessment schedule ([Table 8-2](#)) or as close to the designated day/time as possible. Missed or rescheduled visits should not lead to automatic discontinuation. Subjects who prematurely discontinue the study for any reason should be scheduled for a visit as soon as possible, at which time all of the assessments listed for the final and safety follow-up visits will be performed. At this final visit, the AE and concomitant medications should be recorded on the case report form (CRF).

Table 8-2 Assessment Schedule

Period	Screening	Treatment		EOT		Safety Follow-up					EOS
Cycle		Cycle 1	Cycle 2								
Visit Name	Screening	Treatment C1D1	Treatment C2D1	EOT	Surgery	Safety Follow-up 1	Safety Follow-up 2	Safety Follow-up 3	Safety Follow-up 4	Safety Follow-up 5	EOS
Days	-28 to -1	1	22	When applicable ⁶	4 to 6 weeks	From EOT: 26	From EOT: 52	From EOT: 78	From EOT: 104	From EOT: 130	-
Non-drug therapies and procedures	From 28 days prior to day 1 until 130 days after EOT or start of new antineoplastic therapy, whichever is sooner. After start of a new antineoplastic therapy, only report non-drug therapies for AEs/SAEs suspected to be related to study treatment.										
Adverse Events	Continuous, up to 130 days after last dose of study treatment. After starting a new antineoplastic therapy, only report AEs suspected to be related to study treatment.										
Serious Adverse Events	Continuous, up to 130 days after last dose of study treatment. After starting a new antineoplastic therapy only report SAEs suspected to be related to study treatment.										
Serum Pregnancy Test	X			X							
Urine Pregnancy Test ²		S	S			S		S		S	
PET-CT (with diagnostic quality CT)	X			To be performed within 7 days prior to surgery							
CT/MRI - Thorax, Abdomen, Pelvis (if no diagnosis PET-CT captured)	X			To be performed within 7 days prior to surgery							

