8.4 Safety

Safety assessments are specified below and will be monitored by assessing physical examination, ECOG PS, vital signs, body weight, ECG, laboratory assessments, pregnancy tests, as well as collecting AEs at every visit. For details on AE collection and reporting, refer to AE section. All safety assessments should be completed as per [Table 8-2](#).

Table 8-3 Assessments & Specifications

Assessment	Specification
Physical examination	At screening (within 10 days before cycle 1 day 1), a complete physical examination will include the examination of general appearance, skin, neck (including thyroid), eyes, ears, nose, throat, lungs, heart, abdomen, back, lymph nodes, extremities, vascular, and neurological. If indicated based on medical history and/or symptoms, rectal, external genitalia, breast, and pelvic exams will be performed.

Assessment	Specification
	After randomization (at C1D1 and all following visits) a short physical exam will include the examination of general appearance and vital signs (including blood pressure [SBP and DBP] and pulse). . Information for all physical examinations must be included in the source documentation at the study site. Clinically relevant findings that are present prior to signing informed consent must be recorded on the appropriate CRF that captures medical history. Significant findings made after signing informed consent which meet the definition of an AE must be recorded as an AE.
Vital signs	Vital signs must include at minimum: systolic and diastolic blood pressure (supine position preferred when ECG is collected), respiratory rate, pulse rate and body temperature.
Height and weight	Height in centimeters (cm) or inches (in) and body weight (to the nearest 0.1 kilogram (kg) or pounds (lb) in indoor clothing, but without shoes) will be measured as specified in Table 8-2 .
ECG	Local single 12-lead ECGs should be recorded at baseline prior to the dose administration, after the subject has been resting for 5-10 min.

Post-treatment discontinuation

All safety assessments (including pregnancy test for female subjects of child bearing potential) should be completed as per [Table 8-2](#). However, if the subject begins post-treatment antineoplastic medication before the completion of the 130-Day safety follow-up visit, only the new SAEs and AEs suspected to be related to study treatment will be collected up to the 130-Day safety follow-up visit. Data collected should be added to the appropriate eCRF.

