12.5.2 Safety endpoints

For all safety analyses, the safety set will be used. All listings and tables will be presented by treatment group.

Safety summaries (tables, figures) include only data from the on-treatment period with the exception of baseline data which will also be summarized where appropriate (e.g. change from baseline summaries). In addition, a separate summary for death including on treatment and post treatment deaths will be provided. In particular, summary tables for AEs will summarize only on-treatment events, with a start date during the on-treatment period (treatment-emergent AEs).

The overall observation period will be divided into three mutually exclusive segments:

1. Pre-treatment period: from day of subject's informed consent to the day before first dose of study medication
2. On-treatment period: from day of first dose of study medication to 130 days after last dose of study medication
3. Post-treatment period: starting at day 131 after last dose of any component of the study treatment.

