### **2.7.1 Adverse events (AEs)**

AE summaries will include all AEs occurring during on treatment period. All AEs collected in the AE (e)CRF page will be listed along with the information collected on those AEs e.g. AE relationship to study treatment, AE outcome etc. AEs with start date outside of on-treatment period will be flagged in the listings.

AEs will be summarized by number and percentage of subjects having at least one AE, having at least one AE in each primary system organ class (SOC) and for each preferred term (PT) using MedDRA coding by treatment arm. A subject with multiple occurrences of an AE will be counted only once in the respective AE category. A subject with multiple CTCAE grades (version 5.0) for the same preferred term will be summarized under the maximum CTCAE grade recorded for the event. AE with missing CTCAE grade will be included in the 'All grades' column of the summary tables.

In AE summaries, the primary system organ class will be presented alphabetically and the preferred terms will be sorted within primary SOC in descending frequency. The sort order for the preferred term will be based on their frequency in the canakinumab monotherapy arm.

The following adverse event summaries will be produced by treatment arm:

- Overview of adverse events and deaths
- AEs by SOC and PT (all AEs and AEs related to at least one study drug component)

- AEs by PT (all AEs and AEs related to at least one study drug component) and maximum CTC grade
- AEs leading to permanent discontinuation of one of the study drug component, AEs leading to canakinumab permanent discontinuation
- AEs leading to dose interruption
- AEs requiring additional therapy
- SAEs (all SAEs and SAEs related to at least one study drug component) and SAEs leading to fatal outcome.
- Summary of SAEs and non-SAEs with number of occurrences (an occurrence is defined as >1 day between start and prior end date of record of same preferred term).

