### **2.7.3 Laboratory data**

When analyzing laboratory related date, all sources (central and local laboratories) will be combined. The summaries will include all assessments available for the laboratory parameters collected no later than 130 days after the last study treatment administration date (see [Section](#)

**2.1.3).** Grading of laboratory values will be assigned programmatically as per NCI Common Terminology Criteria for Adverse Events (CTCAE) version 5.0.

The following summaries will be produced for hematology and biochemistry laboratory data (by laboratory parameter and treatment):

- Worst post-baseline CTC grade (regardless of the baseline status). Each subject will be counted only for the worst grade observed post-baseline.
- Shift tables using CTC grades to compare baseline to the worst on-treatment value (hypo and hyper worst grade will be summarized separately if applicable)
- For laboratory tests where CTC grades are not defined, shift tables using the low/normal/high/(low and high) classification to compare baseline to the worst on-treatment value.
- If there are multiple assessments as baseline candidate, the central lab assessment will be defined as “baseline”. If there are multiple assessments from the central lab or the local lab, the worst assessment will be defined as “baseline.”

The following listings will be produced for the laboratory data:

- Listings of all laboratory data, with CTC grades and classification relative to the laboratory normal range. Lab data collected during the post-treatment period will be flagged.
- Listing of all CTC grade 3 or 4 laboratory toxicities

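### All-causality safety summaries run to 130 days after last dose, but unrelated AEs and SAEs stop being collected once new antineoplastic therapy starts, and laboratory summaries have no matching cut

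*SAP*

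**What the plan says.** **Analysis window.** SAP 2.1.3.10 takes as on-treatment the time "from date of first administration of study treatment to 130 days (approximately five terminal half-lives of canakinumab/pembrolizumab) after the date of last administration". Protocol 12.5.2 has the same window: "On-treatment period: from day of first dose of study medication to 130 days after last dose of study medication". Neither ends it at new antineoplastic therapy. SAP 2.7.1 then states: "AE summaries will include all AEs occurring during on treatment period".

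**AE and SAE collection.** Protocol Table 8-2 narrows collection for AEs, "After starting a new antineoplastic therapy, only report AEs suspected to be related to study treatment", and for SAEs, "After starting a new antineoplastic therapy only report SAEs suspected to be related to study treatment". Protocol 8.4, on the period after treatment discontinuation, says that once post-treatment antineoplastic medication has begun, "only the new SAEs and AEs suspected to be related to study treatment will be collected up to the 130-Day safety follow-up visit". Section 10.1.3 has the same limit for SAE reporting. By contrast, Protocol 9.1.1 and 10.1.1 require AE follow-up for at least 130 days after last dose and mention no such exception.

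**Laboratory data.** SAP 2.7.3 includes all available values, central and local, "collected no later than 130 days after the last study treatment administration date". Protocol 8.4.1 ties testing to the visit schedule and states no stop at new therapy. Post-treatment blood biomarker samples do stop at that point (Protocol 8.5.2).

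**New therapy data.** Antineoplastic therapies are recorded at the safety follow-up visits (Table 8-2) and the medications are summarised (SAP 2.4.2). No safety summary uses their start date.

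**The concern.** A percentage in an all-causality AE table is read as the share of treated subjects who had the event in the stated window. Here the window is fixed, but from some subject-specific day only events judged related are collected. After that day, capture depends on a causality judgement by investigators who know the arm, because the study is open-label. Events judged unrelated are absent by design, and nothing in the tables shows it.

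Laboratory values would move the other way. A low neutrophil count or raised ALT measured during adjuvant treatment would enter the worst-grade and shift tables as an on-treatment value of the study drug.

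Post-surgical therapy is foreseeable. Protocol 1.1.1 describes adjuvant treatment as in use in this disease, and the CRF collects it. Safety is a secondary objective, so the effect falls on the safety tables and not on the MPR analysis.

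**Working it through.** **The plan's own figure.** Canakinumab half-life is 26 days (Protocol 4.2.1): 5 × 26 = 130 days, as stated. The documents give no half-life for pembrolizumab.

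**Calendar, for a subject on schedule**
- Last dose: Day 22 (Protocol Table 6-4).
- Window end: 22 + 130 = Day 152, so 152 days from Day 1.
- Surgery 4 to 6 weeks after first dose (Protocol 3): Day 29 to Day 43.

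**Assumption.** Adjuvant therapy starts 4 to 8 weeks after surgery. The documents give no timing.
- Earliest start: 29 + 28 = Day 57. Days affected: 152 − 57 + 1 = 96; 96/152 = 63%.
- Latest start: 43 + 56 = Day 99. Days affected: 152 − 99 + 1 = 54; 54/152 = 36%.

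**Illustration of the effect on incidence (all inputs assumed).** Let F be the true all-causality incidence over 152 days under a constant hazard, f the share of subjects starting new therapy, and d the days of complete collection. Suppose that every event after the start is judged unrelated. Then

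h = −ln(1 − F)/152, and recorded incidence = (1 − f)F + f(1 − e^(−hd)).

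With F = 30%, h = 0.002347 per day.

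| New therapy starts | d | 1 − e^(−hd) | Recorded, f = 20% | Recorded, f = 60% | Shortfall (points) |
|---|---|---|---|---|---|
| Day 57 | 56 | 12.3% | 26.5% | 19.4% | 3.5 to 10.6 |
| Day 99 | 98 | 20.5% | 28.1% | 24.3% | 1.9 to 5.7 |

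With f = 0 the shortfall is zero.

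**Scheduled laboratory visits exposed.** EOT falls 0 to 21 days after last dose (Day 22 to 43) and before surgery (Table 8-1). Follow-up 2 and 4 are calls, and urinalysis is at follow-up 1, 3 and 5 (Protocol 6.5.2.2). I assume that blood tests follow the same three visits; this should be checked against the laboratory rows of Table 8-2, which I could not see.
- Follow-up 1 is EOT + 26 days. Because EOT precedes surgery, this nominally comes before any start at least 28 days after surgery.
- Follow-up 3 is EOT + 78 days, Day 100 to 121: inside the window and after every assumed start.
- Follow-up 5 is EOT + 130 days, Day 152 to 173, with a window of +14 days only: outside unless EOT is on the day of last dose.

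Nominally, then, one scheduled laboratory visit is exposed, plus any unscheduled or local tests.

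**The case against.** The strongest reply is that the plan already contains the remedy. Treatment-related AE and SAE tables are specified and are unaffected by the collection rule. Laboratory data are listed in full, antineoplastic medications since discontinuation are tabulated, and no inferential safety comparison between arms is planned. The SAP also reproduces the protocol's window, so the two documents do not disagree on it. All this is correct and limits the damage, but the all-causality percentages remain incomplete and unlabelled.

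A second reply is that truncation does not cure under-recording. That stands. It recovers no missed event, it removes late suspected-related events from the all-causality tables, and it leaves unequal time at risk. Its merit is that the table then describes a period in which collection was complete.

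A reader might also infer more than the documents support:
- **That AE rates are understated as a matter of fact.** The share and timing of new therapy are not given.
- **That laboratory values are contaminated throughout the 54 to 96 days.** Nominally one scheduled visit is involved. Continued collection is itself inferred, since Protocol 8.4 could be read as stopping other safety data.
- **That contaminated laboratory values feed the canakinumab AESI tables.** AESIs are MedDRA groupings of reported AEs (SAP 2.7.1.1), not laboratory results.
- **That the comparison between arms is biased.** That requires arms to differ in use or timing of new therapy, which is possible but not shown.

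**Conclusion.** The mismatch between collection and analysis is established from the text. For any subject who starts new antineoplastic therapy within 130 days of last dose, all-causality AE, SAE and AESI incidence over the window is incompletely ascertained. Under the assumed start, 36% to 63% of that subject's 152-day window is affected. The effect on a table percentage cannot be fixed from the documents; the illustration gives a shortfall of about 2 to 11 points at 30% true incidence when 20% to 60% of subjects start.

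The laboratory part is conditional. If testing continues after new therapy, the summaries will count those values as on-treatment. Treatment-related AE tables and the primary endpoint are not affected.

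**What to change.** 1. In SAP 2.1.3.10, 2.7.1 and 2.7.3 (and 2.7.4.2 for vital signs), summarise all-causality AEs, SAEs and AESIs, laboratory values and vital signs up to the earlier of 130 days after last dose and the day before new antineoplastic therapy. Report time at risk by arm.
2. Keep the full 130-day window for treatment-related AEs, treatment-related SAEs and deaths. All-causality SAEs do not belong here, because unrelated SAEs also stop being collected. For the same reason, deaths should be confirmed from the study disposition record.
3. Define new antineoplastic therapy for this flag so that the planned resection does not count. Protocol 8.4 speaks of medication, whereas SAP 2.6.2 includes surgery and radiotherapy for best overall response.
4. Record the departure from Protocol 12.5.2 in SAP section 4, which now reads as not applicable.
5. Reconcile Protocol 9.1.1 and 10.1.1 with Table 8-2, 8.4 and 10.1.3, and state whether laboratory collection continues after new therapy.

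The cost is one derived flag and some wording; the start dates are already collected (SAP Table 2-2 uses them). The downside is shorter all-causality follow-up that differs between subjects, with no recovery of uncollected events.

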If the event worsens the event should be reported a second time in the CRF noting the start date when the event worsens in toxicity. For grade 3 and 4 AEs only, if improvement to a lower grade is determined a new entry for this event should be reported in the CRF noting the start date when the event improved from having been Grade 3 or Grade 4.

Conditions that were already present at the time of informed consent should be recorded in medical history of the subject.

AEs (including lab abnormalities that constitute AEs) should be described using a diagnosis whenever possible, rather than individual underlying signs and symptoms.

AE monitoring should be continued for at least 130 days following the last dose of study treatmentOnce an adverse event is detected, it must be followed until its resolution or until it is judged to be permanent (e.g. Continuing at the end of the study), and assessment must be made at each visit (or more frequently, if necessary) of any changes in severity, the suspected relationship to the interventions required to treat it, and the outcome.

Progression of malignancy (including fatal outcomes), if documented by use of appropriate method (for example, as per RECIST criteria for solid tumors), should not be reported as a SAE, except if the investigator considers that progression of malignancy is related to study treatment.

AEs separate from the progression of malignancy (i.e. deep vein thrombosis at the time of progression or hemoptysis concurrent with finding of disease progression) will be reported as per usual guidelines used for such events with proper attribution regarding relatedness to the drug.

Information about adverse drug reactions for the investigational drug can be found in the IB.

Abnormal laboratory values or test results constitute AEs only if they fulfill at least one of the following criteria:

- they induce clinical signs or symptoms
- they are considered clinically significant
- they require therapy

Clinically significant abnormal laboratory values or test results must be identified through a review of values outside of normal ranges/clinically notable ranges, significant changes from baseline or the previous visit, or values which are considered to be non-typical in subjects with the underlying disease.

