12.5.2.1 Adverse events

Summary tables for AEs will include only AEs that started or worsened during the on-treatment period, the treatment-emergent AEs.

The incidence of treatment-emergent AEs (new or worsening from baseline) will be summarized by system organ class and/or preferred term, severity (based on CTCAE v5.0) and relationship to study treatment.

SAE, non-serious AEs and AESI during the on-treatment period will be tabulated. AESIs will be defined based on the case retrieval strategy (CRS) available at the time of the analysis.

All deaths (on-treatment and post-treatment) will be summarized overall and separately.

All AEs, deaths and SAEs (including those from the pre and post-treatment periods) will be listed and those collected during the pre-treatment and post-treatment period will be flagged.

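### Protocol 12.5.2 and the SAP select treatment-emergent AEs by start date alone, so a pre-treatment Grade 3/4 event that improves on treatment can be tabulated as treatment-emergent, contrary to protocol 12.5.2.1

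*SAP*

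**What the plan says.** **Selection by start date.** SAP 2.1.3.10 sets the on-treatment period "from date of first administration of study treatment to 130 days" after the last administration. It then says that AE tables "will summarize only on-treatment events, with a start date during the on-treatment period", and labels these events treatment-emergent. Protocol 12.5.2 carries almost the same sentence. SAP 2.7.1 adds that "AE summaries will include all AEs occurring during on treatment period". None of these places compares an event's grade with its grade before treatment.

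**Selection by new or worse.** Protocol 12.5.2.1 restricts the tables to AEs that began or got worse on treatment, and continues: "The incidence of treatment-emergent AEs (new or worsening from baseline) will be summarized".

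**How entries arise.** Protocol 10.1.1: "For grade 3 and 4 AEs only, if improvement to a lower grade is determined a new entry for this event should be reported in" [case report form]; that entry is dated at the improvement. A worsening also gets its own dated entry. Conditions that already exist at consent go to medical history instead.

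**Other SAP 2.7.1 rules that touch the point.** A subject with several grades of one preferred term "will be summarized under the maximum CTCAE grade recorded for the event". For listings, "AEs with start date outside of on-treatment period will be flagged in the listings". For the table of SAE and non-SAE occurrences only, "an occurrence is defined as >1 day between start and prior end date of record of same preferred term".

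SAP section 4 declares no change to the analyses specified in the protocol.

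**The concern.** A start-date rule works as a test of emergence only if a new start date means that something new or worse has happened. The CRF convention breaks that link in one case: improvement from Grade 3 or 4 also generates a start date. If the event began before the first dose and improves after it, the improvement entry passes the start-date test although the subject is recovering from something that pre-dates study drug.

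The AE tables would then show a recovery as emergent toxicity, and protocol 12.5.2.1 would exclude the same subject from the same row. Type, frequency and severity of AEs is a stated secondary endpoint. With arms of this size a single subject is visible in a table row, so the definition should not depend on which of two protocol paragraphs the programmer follows.

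**Working it through.** The documents give no figure to reproduce; the check is one of logic, followed by a scale.

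**Inputs.** First dose on day 1 and second dose on day 22 (protocol Table 6-4). The on-treatment window is therefore days 1 to 22 + 130 = 152. CRF entry rules are from protocol 10.1.1.

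**Rule S** (protocol 12.5.2, SAP 2.1.3.10 and 2.7.1): an entry counts if its start date lies in the window. The grade shown is the maximum over the on-treatment entries; taking only those entries is my reading.

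**Rule N** (protocol 12.5.2.1, baseline sentence): an entry counts if its start date lies in the window and its grade exceeds the grade of the same event at first dose, taken as 0 for a new event.

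Both rules applied to seven hypothetical sequences of entries for one event:

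| Sequence | Rule S | Rule N |
|---|---|---|
| A. Grade 3 from day −5, improves to Grade 2 on day 10 | counted, Grade 2 | not counted |
| B. Grade 4 from day −5, improves to Grade 3 on day 10 | counted, Grade 3 | not counted |
| C. Grade 2 from day −5, improves to Grade 1 on day 10 (no new entry) | not counted | not counted |
| D. Grade 2 from day −5, worsens to Grade 3 on day 10 | counted, Grade 3 | counted |
| E. New Grade 2 on day 10 | counted, Grade 2 | counted |
| F. Grade 3 from day −5, improves to Grade 2 on day −2 | not counted | not counted |
| G. Grade 3 from day −5, Grade 2 on day 10, Grade 3 again on day 15 | counted, Grade 3 | not counted |

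The rules disagree on A, B and G only. Each is a Grade 3/4 event that starts after consent, is unresolved at first dose and improves on treatment. New and worsened events (D, E) are handled alike.

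Sequence G exposes a second ambiguity. The event worsened between day 10 and day 15, so the opening sentence of protocol 12.5.2.1 would count it. It never exceeded its baseline grade, so the next sentence would not.

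**Do other SAP rules catch A and B?** The listing flag also uses start date, so it marks the pre-treatment entry but not the improvement entry. The rule that joins adjacent entries of one preferred term is stated only for the occurrence table. Neither removes the entry from an incidence table.

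**Scale.** About 110 subjects at 2:2:1 gives 110 × 2/5 = 44, 44 and 110 × 1/5 = 22. One affected subject adds at most 1/44 = 2.3 points in either canakinumab arm, or 1/22 = 4.5 points in the pembrolizumab arm. SAP 2.7.1 counts a subject once per category, so the addition appears only in rows where that subject has no other on-treatment event.

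**The case against.** **The SAP follows the protocol.** A reader might infer that the SAP departs from the protocol and that the two documents give different counts. They do not support that reading: SAP 2.1.3.10 reproduces protocol 12.5.2 nearly word for word. The conflict lies first inside the protocol, between 12.5.2 and 12.5.2.1, and the SAP inherits one side of it. This objection stands, and it determines where the repair must start.

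**The SAP speaks of events, not CRF rows.** Protocol 10.1.1 describes the improvement entry as belonging to the same event, whose onset was before treatment. A programmer who works at event level would not count it. This stands in part: the miscount is possible, not certain. But the SAP gives no linking rule for the incidence tables, and the event-level reading is nowhere required.

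**Cases will be rare.** Conditions present at consent are medical history. Eligibility requires fitness for surgery, ECOG 0 or 1 and adequate organ function, and excludes severe uncontrolled conditions. Nor does every subject undergo a biopsy during screening, since archival tissue up to 5 months old is accepted. All of this stands. The route remains open, because AEs are recorded from consent and screening can last 28 days.

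**Little is distorted.** Randomization takes place at C1D1 before dosing, so pre-treatment events arise independently of arm. Any error overstates toxicity, the analyses are descriptive, and the pre-treatment entry is flagged in the listings. The any-AE row may well not move, because the window runs to 130 days after the last dose and takes in surgery. This stands and keeps the point minor.

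**Conclusion.** The point holds as a minor one. The plan contains two definitions of a treatment-emergent AE, and the CRF rule for improving Grade 3/4 events makes them differ. Under the start-date definition, read entry by entry, a pre-treatment Grade 3/4 AE that improves on treatment can be tabulated as treatment-emergent; protocol 12.5.2.1 excludes it.

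The effect per subject is at most 2.3 points in an arm of 44 and 4.5 points in an arm of 22. These are planned sizes. SAP section 1 reports that recruitment was halted, and neither document gives the resulting Safety Set sizes; smaller arms would raise the effect per subject. The number of affected subjects cannot be estimated, because the documents give no rate of Grade 3/4 AEs in screening, so multiplying these figures by an assumed count per arm would have no basis. SAE and AESI tables are affected only if the improvement entry carries the relevant flag, and related-AE tables only if a pre-dose event was attributed to study drug.

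MPR and the proof-of-efficacy criteria are untouched, and no between-arm bias is expected.

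**What to change.** 1. Reconcile protocol 12.5.2 with 12.5.2.1 so that one definition of treatment-emergent applies.
2. In SAP 2.1.3.10 and 2.7.1, state that consecutive CRF entries of the same event are linked before tabulation. The documents describe no identifier for this; the gap rule that SAP 2.7.1 already uses for the occurrence table could be extended to the incidence tables.
3. State there that an AE is treatment-emergent only if the event is new on treatment or its on-treatment grade exceeds its grade at first dose. Entries opened only because a pre-treatment event improved then drop out.
4. Settle sequence G explicitly. One option is to count re-worsening after an on-treatment improvement as worsening on treatment, which follows the opening sentence of protocol 12.5.2.1.
5. State how missing grades are handled: for example, keep a new event without a grade in the all-grades column, as SAP 2.7.1 already does, and name a default for a pre-treatment event whose grade is missing.

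The cost is one or two SAP sentences, a matching clarification in the protocol, and a small record-linking step in the AE dataset. Sequences D and E show that the new condition in item 3 loses no new or worsened event; only sequence G needs the explicit choice in item 4.
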